NON-INTERVENTIONAL (NI) STUDY PROTOCOL

PASS information

Title	Post-Authorisation Safety Study of Comirnaty Original/Omicron BA.1 and Comirnaty Original/Omicron BA.4-5 in Europe
Protocol number	C4591052
Protocol version identifier	V3.0
Date	08 January 2024
EU Post Authorization Study (PAS) register number	Study to be registered prior to start of data collection.
Active substance	
Riltozinameran (ATC code J07BX03) is a single-stranded, 5'-capped messenger RNA (mRNA) produced using cell-free in vitro transcription from the corresponding DNA templates, encoding the viral spike (S) protein of SARS-CoV-2 (Omicron BA.1).
 
Famtozinameran (ATC code J07BX03) is a single-stranded, 5'-capped messenger RNA (mRNA) produced using cell-free in vitro transcription from the corresponding DNA templates, encoding the viral spike (S) protein of SARS-CoV-2 (Omicron BA.4-5).

Medicinal product	Comirnaty Original/Omicron BA.1 and Comirnaty Original/Omicron BA.4-5
Marketing Authorization Holder(s) (MAH)	BioNTech Manufacturing GmbH
Joint PASS	No

090177e19fa902a7Approved\Approved On: 12-Jan-2024 21:20 (GMT)

PFIZER CONFIDENTIAL

Research question and objectives	
The research question is: Is there an increased risk of pre-specified adverse events of special interest (AESIs) after vaccination with Comirnaty Original/Omicron BA.1 (bivalent BA.1) or Comirnaty Original/Omicron BA.4-5 (bivalent BA.4-5) compared with no vaccination against COVID-19 among individuals with comparable vaccination history?
 
Primary objective
 
To determine whether there is an increased risk of pre-specified AESIs following the administration of bivalent BA.1 or bivalent BA.4-5 compared with not receiving any COVID-19 vaccine during follow-up.

Country(-ies) of study	Italy (IT), The Netherlands (NL), Norway (NO), Spain (ES), United Kingdom (UK)
Authors	[name], [name], [name], RTI Health Solutions, Barcelona, Spain [name], University Medical Center Utrecht, Utrecht, The Netherlands

Marketing Authorization Holder(s)

Marketing Authorization Holder(s)	BioNTech Manufacturing GmbH [name]
MAH contact person	[name]

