7. RATIONALE AND BACKGROUND

In November 2021, World Health Organization (WHO) designated the severe acute respiratory syndrome coronavirus 2 (SARS-CoV-2) variant B.1.1.529 as a variant of concern and named it Omicron.³ The Omicron variant, and its descendant sub-lineages, eg, BA.4-5, have since spread to become the dominant circulating variant worldwide.⁴ The Omicron variant has greatly increased transmissibility and immune-evasion capacity compared with prior circulating variants.⁵ In addition, there is evidence that the original mRNA vaccines provide lower protection against the Omicron variant.⁶⁻⁸

PFIZER CONFIDENTIAL

CT24-WI-GL02-RF02 4.0 Non-Interventional Study Protocol Template For Secondary Data Collection Study
 01-Jun-2022

Page 15 of 64

090177e19fa902a7Approved\Approved On: 12-Jan-2024 21:20 (GMT)

Pfizer-BioNTech has developed bivalent formulations (Comirnaty Original/Omicron BA.1 (bivalent BA.1) and Comirnaty Original/Omicron BA.4-5 (bivalent BA.4-5)) of the Coronavirus Disease 2019 (COVID-19) mRNA-based vaccine. On 01 September 2022 and 12 September 2022, bivalent BA.1 and bivalent BA.4-5, respectively, were authorised for use in the European Union as a booster following a primary vaccination series, at least 3 months after the last dose of any COVID-19 monovalent vaccine.⁹⁻¹¹ Bivalent BA.1 is authorised for individuals aged 12 years and older, while bivalent BA.4-5 is authorised for individuals aged 5 years and older.¹² On 06 December 2022, the Emergency Task Force of the European Medicines Agency (EMA) concluded that bivalent BA.4-5 may be used as a primary vaccination series in adults and children who have not been previously vaccinated against SARS-CoV-2.¹

Safety data reported from Vaccine Adverse Event Reporting System (VAERS) and v-safe in the United States up to October 2022 demonstrate a similar safety profile for the bivalent booster as that reported for the monovalent booster.¹³ However, to gain a more complete understanding, safety monitoring of the bivalent Pfizer-BioNTech COVID-19 booster vaccines is needed in European countries.

This non-interventional study is designated as a Post-Authorisation Safety Study (PASS) and is a commitment to the EMA. This study complies with the European Network of Centres for Pharmacoepidemiology and Pharmacovigilance ENCePP¹⁴ and Accelerated Development of VAccine benefit-risk Collaboration in Europe (ADVANCE)¹⁵ codes of conduct.

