9.3. Variables

9.3.1. Exposure

The exposure categories will be as follows (see [Section 9.1.1.2](#) for definition of time zero):

- **Exposed group:** received a dose of the bivalent BA.1 or bivalent BA.4-5 vaccine. During follow-up, individuals can receive Pfizer vaccines as recommended.
- **Unexposed group:** did not receive any dose of the bivalent BA.1 or bivalent BA.4-5 vaccine at time zero and do not receive any COVID-19 vaccine during the study follow-up.

090177e19fa902a7Approved\Approved On: 12-Jan-2024 21:20 (GMT)

Exposure status will be assessed from recorded prescriptions, dispensing, or administration data for bivalent BA.1 or bivalent BA.4-5. The type of vaccine received and date of vaccination should be obtained from all possible sources that capture COVID-19 vaccination, such as pharmacy dispensing records, general practice records, immunisation registers, vaccination records, medical records, or other secondary data sources. Depending on the data source, vaccines may be identified via nationally used product codes where possible.

If the contributing database cannot differentiate between the monovalent, bivalent BA.1, and bivalent BA.4-5 vaccines, a proxy for vaccine identification will be used (eg, the date of each vaccine introduction in the country, or the date when it is expected that the bivalent BA.1 and bivalent BA.4-5 are mostly used).

Each contributing data source will identify vaccination as follows:

Pedianet (IT) Information on COVID-19 vaccination will include date of administration, type of vaccine, and dose. This information will be collected by the paediatrician at each contact with the individual.

PHARMO (NL): Data on vaccination will be obtained from PHARMO's General Practitioner (GP) database. Information on vaccines includes Anatomical Therapeutic Chemical (ATC) code, brand, and date of administration.

Norwegian health registers, NHR (NO): The national, electronic immunisation register (SYSVAK) records an individual's vaccination status and vaccination coverage in Norway. All vaccinations, including COVID-19 vaccinations are notified to SYSVAK without requiring participant consent. In SYSVAK, the following data are registered: individual personal identifier, vaccine name and ATC code, date of vaccination, reason for vaccination ie, health care professional versus risk-group individual, and the centre where the vaccine was administered.

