9.3.5. Subgroups

Analyses in the matched cohort and in the SCRI study will be conducted in subgroups defined by baseline characteristics as follows:

- Pregnant women;
- Women of childbearing potential, defined as aged between 15 and 50 year old;
- Individuals who are immunocompromised;
- Individuals who have comorbidities;
- Individuals who have autoimmune or inflammatory disorders (eg, rheumatoid arthritis, inflammatory bowel disease);
- Prior influenza vaccination in the last 5 years (yes/no);
- COVID-19 primovaccination-defined subgroups:
 - Individuals who have not started primovaccination;
 - Individuals who have completed primovaccination with Pfizer's monovalent vaccine;
 - Individuals who have completed primovaccination with a Pfizer bivalent vaccine;
 - Individuals who have completed primovaccination with a non-Pfizer vaccine;
- COVID-19 booster-defined subgroups:
 - Individuals who have not received any booster;
 - Individuals whose last booster received was a Pfizer monovalent vaccine;
 - Individuals whose last booster received was a Pfizer bivalent vaccine;
 - Individuals whose last booster received was a non-Pfizer vaccine;
- Type of Pfizer bivalent vaccine received at baseline (bivalent BA.1 or bivalent BA.4-5).

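### Where a data source cannot identify the product, the calendar-date fallback in 9.3.1 may blur the BA.1/BA.4-5 subgroup and may count monovalent doses as bivalent, and no analysis is restricted to product-identified doses

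*Protocol*

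**What the plan says.** Protocol 9.3.1 asks for vaccine type and date from every source that captures COVID-19 vaccination, with national product codes where possible. For a database that still cannot distinguish the three products, "a proxy for vaccine identification will be used (eg, the date of each vaccine introduction in the country", with expected predominant use of the bivalents as a second example. Both examples are calendar dates. Neither uses dose number.

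The dates are in Section 7: "On 01 September 2022 and 12 September 2022, bivalent BA.1 and bivalent BA.4-5, respectively, were authorised for use" in the EU "as a booster following a primary vaccination series, at least 3 months after the last dose of any COVID-19 monovalent vaccine". On 6 December 2022 the EMA task force "concluded that bivalent BA.4-5 may be used as a primary vaccination series in adults and children". Section 5, giving the reason for the new study end date, says that bivalent administration ended by August 2023.

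The objective (8.2) pools BA.1 or BA.4-5 against no COVID-19 vaccine. Section 9.3.5 adds a subgroup by "Type of Pfizer bivalent vaccine received at baseline (bivalent BA.1 or bivalent BA.4-5"), and other subgroups that depend on whether earlier Pfizer doses were monovalent or bivalent. Never-vaccinated people are eligible under 9.2.1.1.

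The estimates from each data source are pooled (9.7.1.9, 9.7.2.3). The sensitivity analyses in 9.7.1.11 cover documented infection, recent health care contact and pooling across sources. Section 9.9 names unrecorded vaccination as a cause of exposure misclassification, but not mislabelling of the product.

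**The concern.** A date rule works only if one product replaces another at a known time. Two bivalents that are available together do not meet that condition. In a source that relies on the rule, a type-specific estimate would largely compare calendar periods, and those differ in viral circulation and in who was being vaccinated.

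The monovalent/bivalent boundary has a different consequence. A monovalent dose given after the cut date would put its recipient in the exposed group, in both the cohort and the self-controlled design. If the two formulations carry different risks for an event, the bivalent estimate would move towards the monovalent one. First-ever doses are the clearest case: bivalents were at first authorised only as boosters, while never-vaccinated people are eligible and form their own subgroup.

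**Working it through.** **1. Calendar gaps** (dates from Sections 5 and 7; end of bivalent use taken as 31 August 2023)

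- 1 to 12 September 2022, between the two EU authorisations: 11 days.
- 12 September 2022 to 31 August 2023, both bivalents authorised: 353 days.
- 1 September to 6 December 2022, bivalents authorised as boosters only: 96 days (85 counted from 12 September).
- 6 December 2022 to 31 August 2023, when a first-ever Pfizer dose could be monovalent or BA.4-5: 268 days.

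**2. Which sources might need the fallback** (fields in 9.3.1)

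- Pedianet records vaccine type. NHR, EpiChron and CPRD record vaccine name.
- PHARMO: "Information on vaccines includes Anatomical Therapeutic Chemical (ATC) code, brand, and date of administration". The title table gives "Famtozinameran (ATC code J07BX03") and the same code for riltozinameran, so ATC code alone cannot separate the bivalents. The protocol does not say whether brand there means product or manufacturer.
- SIDIAP lists dose, brand, reason for vaccination and unspecified further vaccination information.

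Active populations in 9.4 (millions): PHARMO general practice 2.0, NHR 5.3, EpiChron 1.3, SIDIAP 5.8, CPRD 13.3; total 27.7. PHARMO plus SIDIAP is 7.8/27.7 = 28%. Pedianet is left out because its population is not stated.

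**3. The plan's own precision figure**

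Table 3 reproduces as RR × exp(±1.96 × √(1/a − 1/n + 1/b − 1/n)), with a = n × p0 × RR and b = n × p0. For n = 1,000,000 per group, p0 = 1/50,000 and RR 2: a = 40, b = 20, standard error 0.274, interval 1.17 to 3.42, as printed. All 27 rows agree to rounding.

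**4. Monovalent doses counted as bivalent** (reaches the primary exposure)

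Let m be the share of doses labelled bivalent that are really monovalent. The documents give no value, so m is assumed. With equal baseline risk, estimated RR = (1 − m) × RR(bivalent) + m × RR(monovalent). For RR(bivalent) = 2, n = 1,000,000 and p0 = 1/50,000:

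| m | RR(monovalent) = 1 | RR(monovalent) = 2 |
|---|---|---|
| 0% | 2.00 (1.17 to 3.42) | 2.00 (1.17 to 3.42) |
| 5% | 1.95 (1.14 to 3.34) | unchanged |
| 10% | 1.90 (1.11 to 3.27) | unchanged |
| 25% | 1.75 (1.01 to 3.03) | unchanged |
| 50% | 1.50 (0.85 to 2.64) | unchanged |

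Here m is the share over the whole exposed group. If only PHARMO and SIDIAP used the fallback, and exposed people were spread like the active populations (an assumption), 25% contamination within them would give m = 0.28 × 0.25 = 7% and RR 2 − 0.07 = 1.93; 50% would give m = 14% and RR 1.86. Random-effects weights would alter these values.

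**5. BA.1 and BA.4-5 swapped** (type subgroup only)

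Assume 30% BA.1 with RR 2 and 70% BA.4-5 with RR 1. The pooled RR is 0.3 × 2 + 0.7 × 1 = 1.30, whatever the labels. If a share q of BA.4-5 doses is labelled BA.1, the BA.1-labelled RR is (0.3 × 2 + q × 0.7 × 1)/(0.3 + q × 0.7):

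- q = 10%: 0.67/0.37 = 1.81
- q = 30%: 0.81/0.51 = 1.59
- q = 50%: 0.95/0.65 = 1.46

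In the other direction, if 10 to 40% of doses labelled BA.4-5 are really BA.1, the BA.4-5 estimate is 1 + 0.1 to 1 + 0.4, that is 1.1 to 1.4 instead of 1.0.

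**The case against.** The fallback is conditional, comes after all recorded product information, and is introduced by way of example. Four of the six sources record vaccine name or type. Operational detail may sit in the SAP, which is not at hand, and in the extraction specifications that statisticians review (9.3.4). Forest plots by source could show an outlying source. Subgroups are run only if the sample size allows (9.7.1.5). All of this limits the reach of the point. It does not remove it: 9.3.1 states the date rule itself, and nothing in the protocol keeps sources that use it out of the type subgroup.

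A reader might infer more than the documents support:

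- **That confusing BA.1 with BA.4-5 corrupts the primary objective.** The objective pools the two, so a swap leaves the person in the exposed group and the pooled estimate unchanged.
- **That only an 11-day window could be labelled BA.1.** The 11 days separate EU authorisations. The rule refers to introduction in each country, and those dates are not given; the study countries also include the UK. National patterns of use are not described either.
- **That PHARMO or SIDIAP will need the fallback.** No source is said to. PHARMO records brand as well as ATC code, and SIDIAP lists more than brand.
- **That first-ever doses before 6 December 2022 are the hardest to classify.** With dose number they are the easier case, because bivalents were then authorised only as boosters. Dose history is already derived for matching (9.1.1.3). First-ever doses after that date stay ambiguous.

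**Conclusion.** The point holds in a conditional form and is worth acting on. In any source that assigns the product by date alone, BA.1 and BA.4-5 may not be separable once both are in use, which affects only the type-of-bivalent subgroup. Monovalent doses given after the cut may also enter the exposed group, which affects the main analysis.

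The size cannot be fixed from the documents. It depends on how many sources use the fallback, on the contamination share, and on how far the products differ in risk. Under the assumptions shown, a true risk ratio of 2.00 falls to between 1.95 and 1.50 for contamination of 5 to 50% when the monovalent effect is null, and does not move when the two effects are equal. The expected-use option changes the balance of errors without removing them: a later cut mislabels fewer monovalent doses but leaves earlier bivalent doses labelled monovalent.

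**What to change.** - **9.3.1:** name the sources that use the fallback and define it by date plus dose number. Do not class first-ever doses before 6 December 2022 as bivalent in those sources. Treat later first-ever doses without a product record as unclassified.
- **9.3.5 and 9.7.1.5:** exclude proxy-classified sources from the BA.1/BA.4-5 subgroup and keep them in the combined-bivalent analysis.
- **9.7.1.11:** add a pooled sensitivity analysis restricted to sources with a product-level vaccine record. This is also the check on monovalent boosters given after launch, which dose number does not resolve.
- **9.9:** list product misclassification as a limitation.

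The cost is wording and one further run of the meta-analysis. The downside is fewer sources and wider intervals in the type-specific subgroup, and some later first-ever doses left unclassified.

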9.3.2. Outcomes

The list of AESIs to be analysed as outcomes and the preferred study design are based on those proposed by the EMA -sponsored ACCESS project (vACCine COVID-19 monitoring readinESS) and also, for consistency, those included in the ongoing PASS of the Pfizer BioNTech COVID-19 monovalent vaccine (EUPAS41623). The AESIs are listed in Table 1 by body system, with the corresponding risk interval and preferred study design (Section 9.1). Clinical validation will be considered for specific AESIs.

Table 1. Safety outcomes: adverse events of special interest (AESIs) with estimated risk intervals and preferred study design

Body system / classification	Adverse event of special interest	Estimated risk interval (days)*	Preferred study design*
Autoimmune diseases	Guillain-Barré syndrome ^a	42	Cohort/SCRI
	Acute disseminated encephalomyelitis	42	Cohort/SCRI
	Narcolepsy ^a	42	Cohort/SCRI
	Acute aseptic arthritis	42	Cohort/SCRI
	Diabetes mellitus type 1	365	Cohort
	(Idiopathic) thrombocytopenia ^a	42 ^a	Cohort/SCRI
	Thrombosis thrombocytopenia syndrome (TTS) ^a	15 ^a	Cohort/SCRI
	Myositis	365	Cohort
Cardiovascular system	Acute cardiovascular injury including microangiopathy	365	Cohort
	Arrhythmia	365	Cohort
	Heart failure	365	Cohort
	Stress cardiomyopathy	365	Cohort
	Coronary artery disease	365	Cohort
	Myocarditis or pericarditis ^a	7; 14; 21	Cohort/SCRI
	Myocarditis ^a	7; 14; 21	Cohort/SCRI
	Pericarditis ^a	7; 14; 21	Cohort/SCRI
Circulatory system	Coagulation disorders: thromboembolism, haemorrhage	28	Cohort/SCRI

PFIZER CONFIDENTIAL

CT24-WI-GL02-RF02 4.0 Non-Interventional Study Protocol Template For Secondary Data Collection Study

01-Jun-2022

Page 23 of 64

090177e19fa902a7Approved\Approved On: 12-Jan-2024 21:20 (GMT)

Table 1. Safety outcomes: adverse events of special interest (AESIs) with estimated risk intervals and preferred study design

Body system / classification	Adverse event of special interest	Estimated risk interval (days)*	Preferred study design*
	Single organ cutaneous vasculitis	28	Cohort/SCRI
	Cerebral venous sinus thrombosis	28 ²⁸	Cohort/SCRI
Hepato-gastrointestinal and renal system	Acute liver injury	365	Cohort
	Acute kidney injury	365	Cohort
	Acute pancreatitis	365	Cohort
	Rhabdomyolysis	365	Cohort
	Glomerulonephritis	365	Cohort
Nerves and central nervous system	Generalised convulsion	42	Cohort/SCRI
	Meningoencephalitis	42	Cohort/SCRI
	Transverse myelitis ^a	42	Cohort/SCRI
	Bell's palsy	42	Cohort/SCRI
Respiratory system	Acute respiratory distress syndrome	365	Cohort
Reproductive system	Secondary amenorrhea	183	Cohort
	Hypermenorrhea	183	Cohort
Skin and mucous membrane, bone and joints	Erythema multiforme	42	Cohort
	Chilblain-like lesions	42	Cohort
Other	Anosmia, ageusia	42	Cohort
	Anaphylaxis ^a	1 ³¹	Cohort/SCRI
	Multisystem inflammatory syndrome	42	Cohort
	Death (any causes)	365	Cohort
	Subacute thyroiditis	365	Cohort
	Sudden death	365	Cohort
Pregnancy outcome, maternal	Gestational diabetes	Any time pregnancy	Sub-cohort
	Preeclampsia	After 20 weeks gestation	Sub-cohort
	Maternal death	Any time pregnancy	Sub-cohort
Pregnancy outcome, neonates. Define design taking trimester into account	Foetal growth restriction	Any time pregnancy	Sub-cohort
	Spontaneous abortions	At spontaneous abortion	Sub-cohort
	Stillbirth	At birth	Sub-cohort
	Preterm birth	At preterm birth	Sub-cohort
	Major congenital anomalies ^a	1 year after birth	Sub-cohort
	Microcephaly	At birth	Sub-cohort
	Neonatal death	At birth	Sub-cohort
Termination of pregnancy for foetal anomaly	At termination	Sub-cohort	

090177e19fa902a7Approved\Approved On: 12-Jan-2024 21:20 (GMT)

Table 1. Safety outcomes: adverse events of special interest (AESIs) with estimated risk intervals and preferred study design

Body system / classification	Adverse event of special interest	Estimated risk interval (days)*	Preferred study design*
	Small size for gestational age	Any time pregnancy	Sub-cohort
Any	Severe COVID-19 ^b	Any	Cohort

SCRI = self-controlled risk interval

* Time zero corresponds to the day of vaccination (i.e., a 42-day risk interval means that individuals are followed from the day of vaccination to day 41). Risk interval based on the ACCESS project results and other publications.

a For these AESI clinical validation will occur.

b Severe COVID-19 defined as either COVID-19 hospitalisation or death

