9.1.2. Self-controlled risk interval design

The SCRI design will be used as a secondary analysis to compare the occurrence of specific AESIs for which the design is recommended.²⁶ Occurrence of an AESI in a specified risk interval following a dose of bivalent BA.1 or bivalent BA.4-5 will be compared with the occurrence of the same AESI in a later interval (control interval), in the same individual. AESIs that are appropriate for this study design are those that are:

[figure not shown]
- rare, with a transient risk after exposure;
- have a constant event rate within the observation periods;
- have an occurrence that does not alter the duration of the observation window.²⁷

The SCRI design will be used to compare the risk of each AESI during a prespecified period following vaccine administration during which there is a hypothesised increased risk of the outcome ('risk period') with a self-matched control period, used to assess the baseline risk of the outcome.

The risk periods proposed for each AESI and the AESIs that will be analysed using the SCRI design are summarised in [Table 1](#).

A prespecified post-vaccination control period will be used for each outcome. The use of a control period after the risk period (rather than the use of a control period before the risk period) avoids bias from outcomes affecting the probability of exposure (eg, the outcome could be a contraindication for vaccination or could delay vaccination) (Figure 1).

Figure 1. Self-controlled risk interval design

T = time, in days.

Note: Example with a risk period of 42 days and a control period of 42 days.

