9.7.1. Cohort design

9.7.1.1. Exposure assignment and follow-up

The main exposure of interest is in the receipt of at least one dose of the bivalent BA.1 or bivalent BA.4-5 vaccine. Individuals will be assigned to each vaccination category according to their data at time zero, as outlined below:

- **Exposed cohort:** Individuals will be assigned to this cohort when they receive a first dose of the bivalent BA.1 or bivalent BA.4-5 vaccine. Individuals will be censored if they receive a non-Pfizer COVID-19 vaccine during follow-up. For the matched comparative analyses individuals will be censored when their matched pair is censored.
- **Unexposed cohort:** Individuals will be assigned to this cohort if they have not received a COVID-19 vaccine at time zero. Individuals will be censored if and when

PFIZER CONFIDENTIAL

they receive a dose of any COVID-19 vaccine during follow-up. Time zero in the unexposed cohort will be the same day when they did not receive a Pfizer-BioNTech COVID-19 vaccine dose. This day will be chosen by calendar matching to the time zero of the corresponding exposed group.

Individuals will be followed from time zero (see [Section 9.1.1.4](#)) until the censoring described above, death, administrative end of follow-up, or end of study period 31 August 2024, whichever occurs first, with pregnancies followed until 30 June 2025 (see [Section 9.7.1.7](#)). For analyses of AESIs with known risk intervals, follow-up will be truncated at the end of the risk interval.

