9.7.2.2. Measures of association

Conditional Poisson regression will be used to estimate incidence rate ratios and their corresponding 95% CIs. AESI for which the SCRI design will be a secondary approach for AESIs, with their risk windows, are specified in [Table 1](#). The control period that will be the same length will follow the risk interval; more details will be provided in the SAP.

The SCRI inherently adjusts for both measured and unmeasured time constant factors such as sex and chronic health conditions with onset before the start of follow-up. Time-varying confounders may be included as covariates in regression models.

Analyses will be conducted in subgroups defined by demographic and clinical characteristics, dose number, and other covariates of interest when feasible.

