9.9. Limitations of the research methods

This study is subject to limitations related to both the study design and to the use of secondary health care data.

A data-related limitation of this study is the reliance on the accuracy of codes and algorithms to identify outcomes. Some outcomes and their dates of occurrence will be validated, but the extent of validation may be limited because of only partial access to medical records. It is

possible that some AESIs may be due to immunisation errors occurring during the administration of the bivalent BA.1 or bivalent BA.4-5 vaccines. This information is not regularly collected and it will not be possible to take these events into account with the current protocol. Exposure identification may be based on pharmacy dispensing records, general practice records, immunisation registers, medical records, or other secondary data sources. How specific COVID-19 vaccine products and dates of vaccination in these data sources will be identified is described in [Section 9.3.1](#). It is possible that vaccination of individuals outside the health care system will not be recorded in secondary EHR databases, thereby leading to potential bias because of exposure misclassification. Additionally, while every effort will be made to capture data on all variables, some data may not be identified or recorded in the data sources.

A study design-related limitation of both the cohort and SCRI designs is that any uncertainty regarding risk periods will lead to misclassification and underestimation of the risk. The estimation of cumulative incidence curves with a time zero starting on the date of the exposure assignment and eligibility assessment will minimise the impact of unknown risk periods, because there is an unvaccinated comparator and evaluation is done over the whole available follow-up.

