A limitation of the cohort design is the potential for residual or unmeasured confounding, as it is unlikely that the data sources will have information on all potential confounders. To address potential confounding, the SCRI, which automatically adjusts for time-invariant confounders, will be used as a secondary approach. However, the SCRI is not well-suited to study outcomes with gradual onset, long latency, or risk periods that are not well known. It also may be subject to bias for outcomes that affect the probability of exposure. The SCRI design will be used as a secondary approach to the cohort design for prespecified AESI with defined risk intervals. Of note, several safety and efficacy studies comparing vaccination vs. no vaccination using a matched cohort design with matching variables similar to those that will be used in this study have been reported, and good adjustment for confounding was obtained.²¹⁻²⁵

The matching procedure in the cohort analysis produces a study population (ie, a set of matched pairs) with a distribution of matching variables representative of the exposed by matching unexposed individuals to exposed individuals based on a prespecified set of baseline variables. Therefore, the cohort analysis estimates the average causal effect in the vaccinated (ie, in a population that has the distribution of matching variables of the vaccinated). If further adjustment via inverse probability weighting is applied, because the weights are estimated and applied to the matched population, the estimated effect will still be the causal effect in a population that has the distribution of matching variables of the vaccinated. The average causal effect in the vaccinated and the average causal effect in the whole population (vaccinated and unvaccinated) should differ only (apart from random variation) if effect modification by any baseline variable exists. This will have to be considered when comparing effect estimates with those from other studies.

Finally, the extrapolation of the study results to other European countries that not participated in the current analyses and non-European countries should be done cautiously if relevant differences in the populations exist.

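### Narcolepsy's 42-day window and its place in the SCRI will miss most triggered cases if diagnosis lags onset by a month or more; the cohort ratio is then attenuated and the SCRI ratio can fall below 1

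*Protocol*

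**What the plan says.** - Section 9.3.2, Table 1: the narcolepsy row reads "Narcolepsy ^a 42 Cohort/SCRI". The superscript marks it for clinical validation. The table footnote explains that "a 42-day risk interval means that individuals are followed from the day of vaccination to day 41".
- Section 9.7.1.1: "For analyses of AESIs with known risk intervals, follow-up will be truncated at the end of the risk interval".
- Section 9.7.2.2, for the SCRI: "The control period that will be the same length will follow the risk interval". Section 9.2.1.2 admits only people whose event falls in the risk or control interval.
- Section 9.1.2 reserves the SCRI for outcomes that are, among other conditions, "rare, with a transient risk after exposure" and have a constant event rate within the observation periods.
- Section 9.9 states that "the SCRI is not well-suited to study outcomes with gradual onset, long latency, or risk periods that are not well known". It also says, of both designs, that "any uncertainty regarding risk periods will lead to misclassification and underestimation of the risk". The mitigation it offers is cumulative incidence over all available follow-up against an unvaccinated comparator.
- In the same autoimmune block of Table 1, type 1 diabetes and myositis have 365 days and cohort only. The narcolepsy row carries no reference of its own; the footnote cites the ACCESS project and other publications for all intervals.

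**The concern.** Section 9.6 identifies events through diagnosis codes and algorithms, so without a further rule the event date is the recorded date. For an outcome that begins gradually and is diagnosed late, a code on days 0 to 41 will often belong to disease that began before vaccination. The one-year exclusion in Section 9.2.2 does not remove these cases, because it looks for an earlier diagnosis and not earlier symptoms. Disease triggered by the dose would tend to be coded after the cohort has been cut, and some of it inside the SCRI control window.

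The truncation also takes away, for this outcome, the mitigation that Section 9.9 relies on when a risk period is uncertain. At stake is false reassurance on a pre-specified event in a post-authorisation safety commitment. A real excess could be reported as a small one, or as an apparent protective effect in the secondary design.

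**Working it through.** **The plan's own figures.** The protocol gives no number for narcolepsy beyond the 42 days. Its precision table (Table 3) is reproducible. For 1,000,000 per group, risk 1 per 100,000 and risk ratio 2, expected cases are 20 and 10. The standard error of the log ratio is √(1/20 + 1/10 − 2/1,000,000) = 0.387, and 2·exp(±1.96 × 0.387) gives 0.94 to 4.27, as printed.

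**Inputs from the protocol.** Risk window W = 42 days (days 0 to 41). Cohort truncated there. Control window of 42 days, read as days 42 to 83 with no gap.

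**Assumptions.** The true onset rate is multiplied by RR = 5 on days 0 to 41 and returns to background afterwards. The background recorded rate is flat. The recorded date is onset plus an exponential lag with mean m. The documents give no lag, so m runs from 43 days (a 30-day median) to 730 days.

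**Formulas.**
- Share of triggered cases coded in the risk window: p1 = 1 − (m/W)(1 − e^(−W/m)).
- Share coded by day t, for t ≥ W: P(t) = 1 − (m/W)(e^(−(t−W)/m) − e^(−t/m)). Then p2 = P(84) − p1 is the control-window share and p3 = P(365).
- Code-dated 42-day cohort ratio: 1 + 4·p1.
- SCRI ratio: (1 + 4·p1)/(1 + 4·p2).
- Code-dated 365-day cohort ratio: 1 + 4·(42/365)·p3.

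**Example, m = 91 days.** p1 = 1 − 2.167 × (1 − 0.630) = 0.199. P(84) = 1 − 2.167 × (0.630 − 0.397) = 0.495, so p2 = 0.296. Cohort: 1 + 4 × 0.199 = 1.80. SCRI: 1.80/2.18 = 0.82. At 365 days p3 = 0.977 and the ratio is 1.45.

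| Mean lag (days) | p1 | p2 | p3 | 42-day cohort | SCRI | 365-day cohort |
|---|---|---|---|---|---|---|
| 43 | 0.36 | 0.40 | 1.00 | 2.45 | 0.94 | 1.46 |
| 91 | 0.20 | 0.30 | 0.98 | 1.80 | 0.82 | 1.45 |
| 183 | 0.11 | 0.18 | 0.85 | 1.43 | 0.82 | 1.39 |
| 365 | 0.06 | 0.10 | 0.61 | 1.22 | 0.87 | 1.28 |
| 730 | 0.03 | 0.05 | 0.38 | 1.11 | 0.91 | 1.17 |

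In every row p2 exceeds p1, which is why the SCRI ratio falls below 1. With zero lag both designs return 5. A lognormal lag (sigma 1) with medians of 30 to 365 days gives a cohort ratio of 2.33 to 1.02 and an SCRI ratio between 0.64 and 0.89, so the pattern does not depend on the exponential shape.

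**What a longer window gains.** Assume a background of 1 per 100,000 person-years and 1,000,000 per group. Expected unexposed cases are 10 × 42/365 = 1.15 in 42 days and 10 in 365 days (0.6 and 5 at half that rate; 2.3 and 20 at twice it). The true excess is 4 × 1.15 = 4.6 cases. By code date, 42 days captures 1.66, 0.92, 0.49, 0.25 and 0.13 of these down the table; 365 days captures 4.60, 4.50, 3.90, 2.81 and 1.73.

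Dividing the captured excess E by √(2B + E), where B is the background count in the window, gives 0.84, 0.51, 0.29, 0.16 and 0.08 for 42 days. For 365 days it gives 0.93, 0.91, 0.80, 0.59 and 0.37. At the shortest lag the two are close, and for a weak effect the order reverses slightly there: p1/√(42/365) = 1.07 against p3 = 1.00. From a three-month lag on, 365 days is clearly better.

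**Dating by onset.** If validated cases found up to day 365 are placed by symptom onset, late coding removes the same share from both groups and the 42-day ratio returns to 5, provided capture does not depend on exposure.

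**The case against.** The strongest objection is that no section of the protocol says narcolepsy begins gradually or is coded late. That is correct. The conflict with Section 9.9 follows only once that clinical premise is granted, and the lag is shown as a range for this reason.

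The choice also has a stated source. Intervals follow ACCESS and other publications, the AESI list follows ACCESS and the monovalent PASS, the SCRI is only secondary, and Section 9.9 admits that uncertain risk periods cause underestimation. This explains the row, but it does not remove the bias.

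Three stronger readings are tempting and are not supported:

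- A reader might infer that both analyses would sit near 1 whatever the truth. At a mean lag of about 1.5 months the cohort still shows about 2.4 for a true 5, and the SCRI passes below 1.
- A reader might infer that validation cannot help because late-coded records are never retrieved. Section 9.7.1.1 truncates follow-up for analysis and sets no limit on chart retrieval. Section 9.9 says some outcome dates will be validated, though partial record access may limit this. The text leaves the rule for narcolepsy open.
- A reader might infer that every vaccinee contributes a full year. Section 9.1.1.4 censors the matched pair when the unexposed member is vaccinated, and Section 9.2.3 allows follow-up to end at the latest available data.

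It is also fair to object that a 365-day window does not restore the ratio. At mean lags of up to about six months the 365-day ratio is lower than the 42-day one. The gain lies in cases captured and in the risk difference.

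**Conclusion.** The point stands in conditional form. If onset-to-code delay averages 1.5 months or more, most triggered narcolepsy is recorded after day 41. A true 42-day ratio of 5 is then seen as about 2.4 to 1.1 in the code-dated cohort and about 0.8 to 0.9 in the SCRI (exponential lag). This rests on an assumed lag, a flat background, a control window that starts at day 42, and the recorded date serving as event date. It also reads narcolepsy's 42 days as a known interval to which the truncation applies.

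Given gradual onset, assigning narcolepsy to the SCRI goes against the protocol's own suitability statement, and the truncation withdraws the mitigation in Section 9.9. The change is worth making, but the row does not make the cohort analysis uninformative at short lags.

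**What to change.** 1. In Table 1, set narcolepsy to cohort only.
2. Add a 365-day cohort estimate by code date, reported mainly as a risk difference, and exempt it from the truncation in Section 9.7.1.1.
3. Keep the 42-day interval, for alignment with ACCESS and the monovalent PASS, as an analysis of validated cases dated by first symptom onset. Search for cases over the available follow-up, up to 365 days.
4. State that symptom onset sets the event date in that analysis and that cases first coded after day 41 are reviewed.

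The cost is one table row, a longer case search in data already being extracted, and a few more charts for a rare event already marked for validation.

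State these limits alongside the results: the 365-day ratio is diluted (about 1.2 to 1.5 for a true 42-day ratio of 5); pairs may be censored before 365 days; and later Pfizer doses are permitted in the exposed group (Section 9.1.1.1), so a late event is harder to attribute to the bivalent dose.
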